#### **PARTICIPANT DISCONTINUATION/WITHDRAWAL FROM THE STUDY**

Participants are free to withdraw from participation in the study at any time upon request. An investigator may discontinue a participant from the study for the following reasons:

- Lost-to-follow up; unable to contact subject
- Any event or medical condition or situation occurs such that continued collection of follow-up study data would not be in the best interest of the participant or might require an additional treatment that would confound the interpretation of the study
- The participant meets an exclusion criterion (either newly developed or not previously recognized) that precludes further study participation

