### **14.0 Withdrawal of Subjects\***

#### **DISCONTINUATION OF STUDY INTERVENTION/EXPERIMENTAL MANIPULATION**

When a subject discontinues using the Sleep Helper skill but does not withdraw from the study, remaining study procedures will be completed as indicated by the study protocol. The investigator or qualified designee will determine if any change in participant management is needed.

The data to be collected at the time of study intervention discontinuation will include the following:

- The reason(s) for discontinuing the participant from the intervention, and methods for determining the need to discontinue
- The participant will be asked to complete the post-interventions assessments, even though not participating in the intervention

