## **PROTOCOL TITLE: Testing mHealth Delivery of Cognitive Behavioral Therapy for Insomnia to Breast Cancer Survivors**

The reason for participant discontinuation or withdrawal from the study will be recorded on the Case Report Form (CRF). The CRF will include the subject ID, the date the subject left the study, who initiated withdrawal (subject vs PI), and reason for withdrawal. Subjects who sign the informed consent form and are randomized but do not receive the study intervention may be replaced. Subjects who sign the informed consent form, and are randomized and receive the study intervention, and subsequently withdraw, or are discontinued from the study, will not be replaced.

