### **LOST TO FOLLOW-UP**

A participant will be considered lost to follow-up if he or she fails to complete the post intervention forms and study staff are unable to contact the participant after 5 attempts.

The following actions must be taken if a participant fails to return post-intervention forms or equipment:

- Before a participant is deemed lost to follow-up, the investigator or designee will make every effort to regain contact with the participant (where possible, up to 5 telephone calls and/or emails, and if necessary, a mailed letter to the participant's last known mailing address or local equivalent methods. These contact attempts will be documented in the participant's study file.
- Should the participant continue to be unreachable, she will be considered to have withdrawn from the study with a primary reason of lost to follow-up.

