#### Analysis of the Primary Endpoint(s)

The ISI is a seven-item questionnaire with response categories from 0-4 (total score 0-28) asking about sleep patterns and specifically characterizing insomnia over the two weeks prior. Our primary analysis endpoint will use this continuous ISI score.

We will test for assumptions of linearity of regression, homogeneity of error variances, independence of error terms, normality of error terms, and homogeneity of regression slopes. We will use analyses of covariance (ANCOVA) to compare the two groups, which controls for baseline ISI values. We will analyze the treatment effect using the intent-to-treat principle. Descriptive statistics will examine differences in baseline variables between completers and dropouts. If important differences are observed (suggesting the data are missing under a “Not Missing at Random” mechanism) or the loss to follow-up rate exceeds 10%, the primary analysis will be tested through multiple imputation of the ANCOVA model, where potential predictors of dropout will be included in the imputation model, e.g., response to a baseline question asking about the degree of motivation of the participants to stay in the study.

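### A randomised woman whom the investigator discontinues from the study has no stated route to a six-week ISI, so a primary outcome can be lost under an intent-to-treat plan (minor, cheap to close)

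*Combined protocol and SAP*

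**What the plan says.** Section 14.0 separates two situations.

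- **Stopping the intervention.** "When a subject discontinues using the Sleep Helper skill but does not withdraw from the study, remaining study procedures will be completed". The request to fill in the post-intervention assessments is listed under this heading.
- **Leaving the study.** "Participants are free to withdraw from participation in the study at any time upon request". The investigator may also discontinue a participant. Loss to follow-up is one ground. A second covers an event or condition that makes further data collection contrary to her interest, or that "might require an additional treatment that would confound the interpretation of the study". The third is: "The participant meets an exclusion criterion (either newly developed or not previously recognized) that precludes further study participation". For a woman who leaves, the case report form holds her ID, "the date the subject left the study, who initiated withdrawal (subject vs PI), and reason for withdrawal". The six-week ISI is not mentioned.

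Under Lost to Follow-up, a participant has that status if she "fails to complete the post intervention forms and study staff are unable to contact the participant after 5 attempts". Up to five calls or emails, and a letter if needed, follow when post-intervention forms or equipment are not returned.

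In section 17.0, Populations for Analyses and Analysis of the Primary Endpoint(s) both commit to intent to treat. Multiple imputation starts on either of two conditions: important baseline differences between completers and dropouts, or "the loss to follow-up rate exceeds 10%, the primary analysis will be tested through multiple imputation of the ANCOVA model".

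**The concern.** Intent to treat needs the outcome of every randomised woman as far as it can be obtained. Here the investigator may end a woman's participation because a further treatment would complicate interpretation, and the plan does not say that her outcome is still sought.

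That ground can depend on the outcome: a woman whose sleep is not improving is more likely to need something else. If her ISI is not collected, a poor score disappears after randomisation. The only imputation predictor the plan gives as an example is a baseline motivation question, and imputing from baseline variables would correct such a loss only in part. Collecting the score therefore matters more than how the trigger is worded.

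The trigger is a lesser issue. If the loss to follow-up rate in section 17.0 takes its meaning from section 14.0, a woman who can be reached but has withdrawn or been discontinued is not lost to follow-up. Her missing ISI then need not count toward the 10%.

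**Working it through.** **1. The plan's own figure.** Inputs from Sample Size Determination: effect 0.65 SD, pre-post correlation 0.5, two-sided alpha 0.05, power 80%. ANCOVA power comes from a noncentral t with N − 3 degrees of freedom and noncentrality 0.65/√(1 − 0.5²) × √N/2. At N = 58 the power is 0.802, so the stated 58 (29 per arm) reproduces. The recruitment target is 76, or 38 per arm.

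**2. Which provision asks for the six-week ISI?**

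| Situation | Provision | Six-week ISI requested? |
|---|---|---|
| Stops the skill, stays in the study | 14.0, discontinuation of intervention | Yes, expressly |
| Forms not returned | 14.0, Lost to Follow-up | Chased; discontinued women neither named nor excluded |
| Discontinued for a possible confounding treatment or an exclusion | 14.0, discontinuation from the study | Not stated |
| Participants in general | 6.0, forms at six weeks | Yes, but not said to continue after leaving the study |

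**3. Size of the bias (assumed inputs).** The documents give no discontinuation rate. Assume a = 3 women removed from one arm and b = 1 from the other, each δ = 0.25 to 0.5 SD worse than the women retained, after baseline adjustment.

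Shift in the contrast = (a − b)/38 × δ

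- δ = 0.25: 2/38 × 0.25 = 0.013 SD, which is 2.0% of 0.65.
- δ = 0.5: 2/38 × 0.5 = 0.026 SD, which is 4.0% of 0.65.
- Equal removals (a = b): 0.
- If half of these women return the form, the remaining shift is 0.007 to 0.013 SD.

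With 29 analysed per arm, 55 degrees of freedom and residual SD √0.75, these shifts give a two-sided type I error of 0.0504 and 0.0515 instead of 0.05.

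A harsher assumption is that 2 to 6 of 38 are removed from one arm and none from the other, at 0.5 to 1.0 SD worse. The shift is then 2/38 × 0.5 = 0.03 up to 6/38 × 1.0 = 0.16 SD, with rejection rates under no effect of about 5.2% to 11.7%. Nothing in the documents points to removals that many or that one-sided.

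**4. The 10% trigger, if read by the section 14.0 definition.**

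- 7/76 = 9.2% does not exceed 10%; 8/76 = 10.5% does.
- With 7 counted losses and 2 uncounted women, 9/76 = 11.8% are missing but the rate reads 9.2%.
- With 2 uncounted, the definition changes the result only at 6 or 7 counted losses. For X ~ Binomial(74, p):

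| Counted-loss rate p | P(X = 6 or 7) |
|---|---|
| 5% | 0.134 |
| 10% | 0.298 |
| 15% | 0.091 |
| 20% | 0.0105 |
| 30% | <0.0001 |

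At the 30% dropout allowed for in the sample size, the wording is irrelevant if most dropouts are unreachable. It would matter if many withdraw while reachable: 15/76 = 19.7% missing, with 7 unreachable, would still read as 9.2%.

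**The case against.** The strongest reply is that the gap is one of silence. The Lost to Follow-up actions apply whenever post-intervention forms are not returned, and section 13.0 offers every participant an incentive for completing them. Neither shuts out a discontinued woman. A reader might infer that the plan forbids collecting her ISI or drops her from the analysis. The documents say neither, and the consent form, which is not in this copy, may say more. What stands is that the one express request is conditional on not having withdrawn from the study, and staff following it have no instruction to ask her.

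Second, a reader might infer that both grounds remove women because they are doing badly. Most of the exclusions in section 10.0 do not work that way: shift work, travel, pregnancy and a late-recognised sleep disorder are not consequences of failing to improve. Starting psychological treatment could be read as a newly met exclusion, but that is one item in an eligibility list, and the exclusion must also be one that precludes further participation. The objection therefore succeeds for most of the exclusion ground and leaves the confounding-treatment ground untouched.

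Third, section 17.0 does not expressly tie its loss to follow-up rate to the definition in section 14.0, and the comparison of completers with dropouts may still start imputation. Both points are right and make the trigger secondary. Still, dropout is undefined, an important difference has no threshold, and neither trigger recovers a score that was never requested.

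Finally, the rule is permissive and the study lasts six weeks, so it may seldom be used. That limits the size of the problem but does not close the gap.

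**Conclusion.** The point holds as a minor weakness. A stated discontinuation rule can cost the primary outcome of a randomised woman, and the intent-to-treat commitment is not linked to any instruction to keep collecting it.

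Under the milder assumptions the shift is about 0.01 to 0.03 SD, with almost no effect on type I error. These figures rest on assumed counts and an assumed gap in outcome. A reader might infer that the bias favours the device. The documents do not support that, because the rule applies to both arms: more removals of non-improving women from the device arm would favour it, more from the control arm would count against it, and equal removals cancel.

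The trigger concern is conditional on reading section 17.0 by the section 14.0 definition. With two uncounted women it matters mainly when counted losses run near 10%.

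**What to change.** 1. In section 14.0, under discontinuation from the study, state that discontinuation for a possible confounding treatment, or for a new or late-found exclusion, does not end outcome collection. The six-week REDCap ISI is still requested unless she withdraws consent or further collection is not in her interest.
2. In section 17.0, Analysis of the Primary Endpoint(s), base the 10% trigger on all randomised women without a six-week ISI, whatever the reason.

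No rule on stopping the intervention changes.

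The cost is a few sentences and a few extra contacts, since the online form already exists. Some discontinued women will still not return it. Some scores will be taken after another treatment has started, which is consistent with intent to treat.

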## **PROTOCOL TITLE: Testing mHealth Delivery of Cognitive Behavioral Therapy for Insomnia to Breast Cancer Survivors**

The reason for participant discontinuation or withdrawal from the study will be recorded on the Case Report Form (CRF). The CRF will include the subject ID, the date the subject left the study, who initiated withdrawal (subject vs PI), and reason for withdrawal. Subjects who sign the informed consent form and are randomized but do not receive the study intervention may be replaced. Subjects who sign the informed consent form, and are randomized and receive the study intervention, and subsequently withdraw, or are discontinued from the study, will not be replaced.

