**PROTOCOL TITLE: Testing mHealth Delivery of Cognitive Behavioral Therapy for Insomnia to Breast Cancer Survivors**

**1.0 STUDY SUMMARY**

Study Title	Testing mHealth Delivery of Cognitive Behavioral Therapy for Insomnia to Breast Cancer Survivors																													
Study Design	Randomized controlled trial																													
Primary Objective	To determine whether the smart speaker group will have significantly greater reductions in insomnia severity compared to the website-based group as recorded by the Insomnia Severity Index (ISI).																													
Secondary Objective(s)	Secondary Objective: To measure differences between intervention and control arms for and CSD metrics																													
Research Intervention(s)/Investigational Agent(s)	In the intervention arm participants will receive an Amazon Dot device with a pre-loaded Sleep Helper program, using an account created by Media Rez (study prime) so Amazon does not have access to participant names (for patient privacy purposes). Participants will be asked to engage with the program daily, either using the voice-activated speakers or an accompanying smart-phone app. The study duration is six-weeks and is completed individually using fully automated interaction to deliver components of cognitive behavioral therapy for insomnia.																													
IND/IDE #	N/A																													
Study Population	We will recruit female breast cancer survivors over age 18. Women must have been diagnosed with stage I-III breast cancer or stage IV with high functioning (Eastern Cooperative Oncology Group status 0-1). Curative treatment (not adjuvant) must have been completed >3 months prior to enrollment.																													
Sample Size	n=76 breast cancer survivors																													
Study Duration for individual participants	Individuals will fill out sleep and medical history forms at baseline and will be randomized to a six-week protocol.																													

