**2.2**

We hypothesize that our program will reduce insomnia measured by the insomnia severity index (ISI) to sub-clinical threshold levels overall (intent to treat analysis). We also will test whether those with higher adherence report greater improvement in insomnia symptoms.

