**5.0 Study Intervention/Investigational Agent**

**Intervention Condition.**

After randomization to the intervention arm participants will receive an Amazon Echo Dot with the Sleep Helper skill and will be asked to enroll either by giving responses to voice prompts for setup or entering baseline information via an accompanying smart phone application. Participants will receive written instructions for how to enroll. The MHRI research team will reach out to participants by email and/or phone after delivery confirmation to ensure that participants have enrolled and initiated the program. Participants will receive written instructions to complete morning, night, relaxation and educational modules daily. Participants will also be instructed on security settings that will be pre-set for maximal security.

**Intake.** At the start of the intervention participants will be provided with written instructions on setting the program up and asked to complete an intake form on background information, which can be completed via the smart phone app. Participants will be able to use a smart phone app to enter standard insomnia intake assessment information that includes sleeping patterns, sleep hygiene practices (e.g. timing and

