**12.0 Local Number of Subjects**

12.1 We plan to enroll up to 76 patients in the study total, with about one third accrued locally.

We anticipate screening approximately 150 women in order to identify n=76 for the RCT.

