### ○ POPULATIONS FOR ANALYSES

For our primary and secondary analyses we will be using intent to treat. In tertiary analyses we will conduct analyses by adherence (median frequency of engagement).

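### The rule that lets randomised women who did not receive the intervention be replaced conflicts with the intent-to-treat analysis, and would probably act mainly on the speaker arm

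*Combined protocol and SAP*

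**What the plan says.** Section 14.0, under participant discontinuation and withdrawal from the study, lists what the case report form records when a woman leaves. It continues: "Subjects who sign the informed consent form and are randomized but do not receive the study intervention may be replaced". The next sentence deals with women who did receive the intervention: those who "subsequently withdraw, or are discontinued from the study, will not be replaced". The section names no arm and does not define receipt. It does not say who decides, how a replacement is allocated, or what happens to the replaced woman's data.

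On analysis, section 17.0 (Populations for Analyses) says: "For our primary and secondary analyses we will be using intent to treat". Under the primary endpoint it adds: "We will analyze the treatment effect using the intent-to-treat principle". Neither place defines the set. The hypothesis in section 2.2 also names intent to treat. On numbers, section 12.1 says: "We plan to enroll up to 76 patients in the study total".

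On starting, section 5.0 gives the speaker arm a device and a set-up step, after which staff will "reach out to participants by email and/or phone after delivery confirmation to ensure that participants have enrolled and initiated the program". Controls get access to a website that they may use as much or as little as they like. No check that they have begun is described.

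**The concern.** Intent to treat keeps every randomised woman in the arm to which she was assigned. The replacement rule is triggered by something that happens after randomisation, and its wording leaves the choice open. If replaced women leave the analysis, the groups compared are no longer the groups that were randomised.

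The arms are not equally exposed to the rule. Failure to receive or start is easy to see where equipment is mailed and set-up is checked, and hard to see where the condition is website access. Anyone who sees set-up status also knows the arm.

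Two things are at stake. First, if never-starters have a worse prognosis than starters, dropping them from one arm biases the comparison even when the treatment does nothing. Second, the estimate moves from the effect of being assigned the speaker towards the effect among women who take it up. Sections 3.0 and 3.3 argue for smart speakers partly because web programs lose people, so failure to start belongs to the trial's question. In addition, replaced women who are not counted would presumably not count towards the 10% loss that triggers multiple imputation in section 17.0.

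**Working it through.** 1. The plan's own figure. Inputs from section 17.0 (Sample Size Determination): d = 0.65, pre-post correlation r = 0.5, two-sided alpha 0.05, power 80%. For ANCOVA the residual SD is sqrt(1 - r²) = sqrt(0.75) = 0.866. With 29 per arm the noncentrality is 0.65 / (0.866 × sqrt(2/29)) = 2.86 on 58 - 3 = 55 degrees of freedom, which gives power 0.802. N = 58 is therefore reproduced, as are all nine cells of the table. With 38 per arm and no loss, power is 0.898.

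2. The enrolment plan. Suppose replaced women stay in the analysis and 38 speaker-arm starters are wanted. The number randomised to that arm must then be 38 / (1 - p), where p is the never-starter share. At p = 10% this is 42.2, about 4 extra. At p = 20% it is 47.5, between 9 and 10 extra. The trial would then exceed the planned maximum of 76. Once 76 women have been randomised, a replacement fits under that maximum only if the woman replaced is not counted.

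3. Bias if never-starters are dropped from the speaker arm only. The documents give neither the never-starter share nor their prognosis. Assume p = 5-20%, and that never-starters' final ISI, adjusted for baseline, is g = 0.25-0.8 SD worse. Controls still contain the same kind of women and the replaced speaker arm does not, so under no treatment effect the bias is p × g in favour of the speaker. The noncentrality is p × g / (0.866 × sqrt(2/38)) = p × g / 0.1987, with 73 degrees of freedom. This takes 76 women analysed and holds the residual SD at 0.866.

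| p | g = 0.25: bias, type I error | g = 0.5 | g = 0.8 |
|---|---|---|---|
| 5% | 0.013, 0.050 | 0.025, 0.052 | 0.040, 0.055 |
| 10% | 0.025, 0.052 | 0.050, 0.057 | 0.080, 0.068 |
| 15% | 0.037, 0.054 | 0.075, 0.066 | 0.120, 0.092 |
| 20% | 0.050, 0.057 | 0.100, 0.079 | 0.160, 0.125 |

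4. Dilution, a separate matter. Assume the effect is 0.65 among starters and zero among never-starters, and that all 76 women are analysed. The effect by assignment is 0.65 × (1 - p): 0.585 at 10% and 0.65 × 0.8 = 0.52 at 20%. Power is then 0.828 and 0.733.

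**The case against.** The strongest reply is that the sentence permits replacement and says nothing about excluding data. Section 17.0 governs the analysis: it prescribes intent to treat, CONSORT reporting, and multiple imputation when loss exceeds 10%. If replaced women are followed and analysed as randomised, intent to treat survives and the rule only adds participants. A reader might infer that the comparison is shown to be broken. The documents do not support that, because exclusion is implied by the withdrawal context and the planned maximum, and is never stated.

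A reader might also infer that only speaker-arm women can be replaced. No arm is named, and the hypotheses in section 17.0 describe what controls get as an intervention too. Receipt may also mean delivery. Section 5.0 uses the word for getting the device, with set-up coming later. On that reading a woman who loses interest after delivery has received the intervention and is not replaced, so the rule reaches only women lost before delivery. A wider reading, receiving the therapy through the skill, is equally open.

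Nor does the primary objective promise intent to treat. Section 1.0 says only "To determine whether the smart speaker group will have significantly greater reductions in insomnia severity compared to the website-based group", and the promise is in the section 2.2 hypothesis and the analysis text. It is also tempting to turn the dilution into a percentage overstatement of the effect. That would compare two different target quantities at an assumed non-start share, and section 17.0 does not describe 0.65 as an effect among starters. The dropout rates cited in sections 3.0 and 3.3 concern other programs and do not measure failure to receive a device. Finally, nothing says that a vacated allocation is reissued.

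These points limit the claim but do not remove it. A stated rule allows discretionary substitution after randomisation, with no criterion and no statement on the data. Section 14.0 asks women who stop using the skill to complete the final assessments, but does not clearly cover those who never began. Even the kindest reading leaves the primary analysis set undefined and sits badly with the planned maximum.

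**Conclusion.** The concern holds in this form: read in its context, the replacement rule conflicts with the intent-to-treat analysis, and it would probably act mainly, not exclusively, on the speaker arm. The documents do not allow the size to be computed. Over the assumed ranges, bias runs from negligible (about 0.01 SD, type I error 0.050) to enough to matter for the primary test (0.16 SD, 0.125). Those figures require never-starters to be dropped from the speaker arm only and to have a worse prognosis. With no prognostic difference there is no bias under the null. The dilution to 0.585-0.52 is a change in what is estimated and should not be read as a bias figure.

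The point goes beyond missing detail, because a stated permission has to be withdrawn.

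**What to change.** Delete the replacement sentence in section 14.0. State in sections 14.0 and 17.0 that:

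- every randomised woman is asked for the six-week forms and analysed in her assigned arm, whether or not she received or started the intervention;
- no allocation is reissued, and any further enrolment takes the next allocation in sequence;
- women who did not start are reported by arm in the CONSORT flow.

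Any woman already replaced should be restored to the intent-to-treat set. This should be settled before the analysis.

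The cost is wording, a few more forms to chase and possibly a smaller estimated effect, with the loss of power shown above if never-starters gain nothing. Replacement is not needed to cover dropout, because section 17.0 already raises 58 to 76 for that purpose. As a separate matter, that step is 58 × 1.3 = 75.4, rounded up, and covers a loss of 18/76 = 23.7% where the plan says 30%. If more margin is wanted, it should come from the sample size and not from replacing randomised women.
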